The UDPB scale is a standardized bleeding definition that was specifically designed by experts to capture early bleeding after cardiac surgery and is based on the following 9 criteria occurring either in surgery or during the first postoperative day: (1) delayed sternal closure, (2) postoperative chest tube output, (3) packed red blood cell transfusion, (4) fresh frozen plasma transfusion, (5) platelet transfusion, (6) cryoprecipitate transfusion, (7) use of factor concentrates, (8) use of recombinant activated factor VII (rFVIIa), and (9) surgical re-exploration. [17] The UDPB scale defines 5 perioperative bleeding classes (0-4) as shown in **Table 1** (below). Importantly, it has been demonstrated that higher classification within the UDPB (starting from moderate, up through severe-massive) is correlated with higher 30-day mortality rate, thus making the standardized definition both a useful descriptive tool as well as a predictor of clinical outcome. [17]

Table 1. Bleeding Class According to the Universal Definition of Perioperative Bleeding in Adult Cardiac Surgery

Class	Sternal Closure delayed	Postoperative chest tube blood loss within 12 h (mL)	PRBC (units)	FFP (units)	PLT (units)	Cryoppt	PCCs	rFVIIa	Reexploration/tamponade
0	No	< 600	0*	0	0	No	No	No	No
1	No	601-800	1	0	0	No	No	No	No
2	No	801-1000	2-4	2-4	Yes	Yes	Yes	No	No
3	Yes	1001-2000	5-10	5-10	N/A	N/A	N/A	No	Yes
4	N/A	>2000	>10	>10	N/A	N/A	N/A	Yes	N/A

Class 0 = Insignificant; Class 1 = Mild; Class 2 = Moderate; Class 3 = Severe; Class 4 = Massive

PRBC = packed red blood cells; FFP = fresh frozen plasma; PLT = platelet concentrates; Cryoppt = Cryoprecipitate; PCCs = prothrombin complex concentrates = rFVIIa, recombinant activated factor VII; N/A, not applicable

For purposes of UDPB, PRBC, PLT, FFP, and Cryoppt transfusions are counted beginning **at chest closure**. PCC and rFVIIa transfusions are counted beginning at the start of the procedure.

* Correction of preoperative anemia or hemodilution only; the number of PRBCs used should only be considered in the UDPB when accompanied by other signs of Perioperative bleeding. Prophylactic/preoperative transfusion of blood products and factor concentrates do not contribute to UDPB.

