Pre-randomization stratification based on a) study site, and b) planned type of cardiothoracic operation will address potential confounding variables that may not be fully controlled in the randomization process. Stratification by site is intended to control for institutional differences in standard practices, such as transfusion and re-operation protocols. Stratification by the type of planned operation will separate subjects undergoing CABG-alone from those undergoing all other cardiothoracic surgeries. The category of “all other” cardiac surgeries includes combination cases (e.g., CABG + valve, double valve, etc.) and ascending aortic interventions. Compared to CABG-alone, these operations have a significantly different profile in regards to bleeding risk and procedure/CPB duration. This distinction is also important since device exposure is directly related to the amount of time spent on CPB. Details of the statistical considerations around the endpoints discussed above will be provided in **Section 11**.

In summary, the objective of the randomized, double-blind investigation outlined in this protocol will be to examine the ability of DrugSorb™-ATR (a non-pyrogenic, sterile, single-use device designed to remove the small hydrophobic drug, ticagrelor) to reduce postoperative bleeding compared to current standard of care. Measurements of drug removal will also be performed to establish that bleeding reductions are related to reductions in ticagrelor levels. The safety of the device in this setting will be assessed by systematic capture of all AEs at the CGP level.

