4.3. Study Outcomes

4.3.1. *Primary Effectiveness Endpoint:*

- Ranked composite of perioperative bleeding events:
 - 1) Fatal perioperative bleeding (occurring within 48hrs post-index procedure),
 - 2) UDPB ≥ 2 perioperative bleeding, and
 - 3) 24-hour chest tube drainage volume (mL).

Refer to **Table 1** for details of the UDPB classification of bleeding events.

4.3.2. *Key Secondary Effectiveness Endpoint:*

- Percent difference in pre-CPB vs. post-CPB blood ticagrelor levels as measured by liquid chromatography/tandem mass spectrometry [LC/MS-MS] (i.e., Δ [ticagrelor]).

4.3.3. *Additional Secondary Effectiveness Endpoints:*

- 24-hour chest tube drainage volume
- Total platelet transfusions during the index hospitalization (volume and units)
- Total PRBC transfusions during the index hospitalization (volume and units)
- Total UDPB events (by class)
- All surgical re-exploration for excessive bleeding
- Total fatal perioperative bleeding events

4.3.4. *Exploratory Endpoint(s):*

- Area under the concentration time curve (AUC), for intraoperative ticagrelor pharmacokinetic (PK) concentration
- Operative time (measured from start of skin incision to completion of chest closure)
- Duration of ICU stay
- Duration of hospital stay
- 30-day hospital readmissions

4.3.5. *Primary Safety Endpoint:*

- The primary safety endpoint of this trial is to evaluate the product safety profile through the GCP-level assessment of AEs during the study period.

4.3.6. *Additional Safety Endpoints:*

- 30-day cardiac mortality
- 30-day all-cause mortality
- Postoperative stroke during the index hospitalization
- Postoperative myocardial infarction (MI) during the index hospitalization
- Urgent postoperative coronary revascularization during the index hospitalization
- Serious device-related adverse events

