5.2. Potential Benefits

The observed and potential benefits of using the DrugSorb™-ATR device intra-operatively during cardiothoracic surgery to remove ticagrelor include:

- Decrease in perioperative bleeding complications; including:
 - Decrease in perioperative blood loss, including that measured in chest/mediastinal drains
 - Decrease in blood product transfusions
 - Reduced risk of re-operation for bleeding
 - Reduced risk of fatal bleeding
- Improvement in hemodynamic stability and reduction in vasopressor requirements
- Decrease in mean operative time including time to hemostasis
- Decrease in the amount of time on a mechanical ventilator
- Decrease in hospital stay following surgery, including time in the ICU

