**1.3.4. Exploratory Endpoints**

- Percent difference in pre-CPB vs. post-CPB blood ticagrelor active metabolite (TAM) levels as measured by LC/MS-MS
- Area under the concentration time curve (AUC), for intraoperative ticagrelor pharmacokinetic (PK) concentration and for TAM
- Operative time (i.e., duration of index operation, measured from start of skin incision to completion of chest closure)
- Duration of ICU stay
- Duration of hospital stay
- 30-day hospital readmissions

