### 1.3.7. Exploratory Subgroup Analyses

The primary effectiveness endpoint and its individual components will be analyzed in the following subgroups:

1. Surgical Characteristics
  - a. Procedure duration (skin incision to closure): <4 hours vs. 4-6 hours vs. >6 hours
  - b. CPB duration (i.e., device exposure):
    - Tertiles
    - Above and below median
2. Drug Removal
  - a. Time from Last Dose:
    1. Tertiles
    2. 0-24 vs. 24-48 vs. >48 hours
    3. above vs below median
    4. 0-24 vs. >24 hours
    5. 0-48 vs. >48 hours
  - b. Ticagrelor Levels
    6. Above vs. Below median pre-CPB levels (whole population)
    7. Above vs. Below median post-CPB levels (whole population)
    8. >67% vs. <67% removal (per intervention arm values)
    9. >50 vs. <50% removal (per intervention arm values)
    10. >40 vs. <40% removal (per intervention arm values)

The key secondary endpoint will be analyzed according to surgical characteristics and the time from last dose subgroups.

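### SAP 1.3.7 item 1a reads the primary endpoint within strata of actual procedure duration, a post-randomization variable that the protocol expects the device to shorten, so the stratum results cannot show effect modification

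*Protocol*

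**What the plan says.** Under the title "Exploratory Subgroup Analyses", SAP 1.3.7 states that "The primary effectiveness endpoint and its individual components will be analyzed in the following subgroups". Item 1a is "Procedure duration (skin incision to closure): <4 hours vs. 4-6 hours vs. >6 hours". The section ends by adding the key secondary endpoint by surgical characteristics, the group that contains item 1a.

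The same quantity is a trial endpoint. Protocol 4.3.4 lists "Operative time (measured from start of skin incision to completion of chest closure", and SAP 1.3.4 has "Operative time (i.e., duration of index operation, measured from start of skin incision to completion of chest closure". Protocol 5.2 lists "Decrease in mean operative time including time to hemostasis" among observed and potential benefits.

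Protocol section 3 bases the UDPB scale on nine "criteria occurring either in surgery or during the first postoperative day: (1) delayed sternal closure, (2) postoperative chest tube output" and others. Table 1 puts delayed sternal closure in class 3, so it counts as a UDPB ≥2 event.

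For operation length, the protocol relies on the planned procedure. It says of the operations other than CABG alone: "Compared to CABG-alone, these operations have a significantly different profile in regards to bleeding risk and procedure/CPB duration". Planned procedure is a randomization stratum (Protocol 6.1) and a protocol subgroup (11.4). CABG against other procedures is on the SAP 3.6 list.

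**The concern.** A subgroup comparison keeps the protection of randomization only if membership is fixed before treatment or cannot be changed by it. Procedure duration fails on the sponsor's own hypothesis: less ticagrelor, faster hemostasis, earlier closure. A control patient may then be in the >6 hour stratum because of bleeding, while a device patient is there more often because the operation was complex. The stratum win ratio mixes the device effect with this difference in case mix.

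At stake is the reading of the table. It invites the statement that the device works in short operations, or in long ones, when differences between strata, or between the strata and the overall result, could arise from the way the strata are formed.

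**Working it through.** **1. Check of the model against the plan's power.** Inputs from SAP Table 1: fatal bleeding 3.0% in both arms; UDPB ≥2 24.3% against 40.5%; 24-hour drainage 480 against 800 mL, SD 253 (Scenario 1, 57 per arm) or 500 (Scenario 2, 65 per arm). The test is that of SAP 5.2.2.1: T = Σ DᵢWᵢ with variance nm/(N(N−1)) · ΣWᵢ², two-sided 0.05, independent components, 4,000 simulated trials.

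- Scenario 1: 99.6% (SAP 99.7%).
- Scenario 2: 91.6% (SAP 92.1%).
- Under the null: 5.2% rejections.

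**2. What the documents do not give.** They contain no distribution of procedure duration, no duration-bleeding link, no expected time saving and no delayed-closure rate. Everything below on duration is an assumption. The win ratio is N_W/N_L, as in SAP 5.2.2.2.

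**3. Scenario 2 illustration.** Duration = 4.7 h + 0.9 h per SD of complexity + g hours per SD of bleeding; latent correlation of UDPB with bleeding 0.6. The device lowers bleeding by (800 − 480)/500 = 0.64 SD, so the implied time saving is 0.64g: 0.26 h at g = 0.4, 0.51 h at 0.8 and 0.77 h at 1.2. The true effect is uniform, and the overall win ratio is about 1.9.

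- g = 0: no attenuation.
- g = 0.4: strata about 1.7-1.8.
- g = 0.8 to 1.2: strata about 1.5-1.7.
- g = 0, delayed closure in 10% of UDPB ≥2 cases: 1.90 / 1.89 / 1.90 against 1.89 overall.
- No bleeding effect, device only shortens surgery: 1.0 overall, strata about 0.57-0.85.

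**4. Scenario 1 illustration, different structure.** Mean duration 5 h, residual SD 1 h. A common bleeding liability drives UDPB, drainage and duration. Delayed closure, where included, affects 10% of UDPB ≥2 cases and adds 24 h.

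| Case | Overall | <4 h | 4-6 h | >6 h | Share >6 h, device / control |
|---|---|---|---|---|---|
| Effect; no link | 2.77 | 2.67 | 2.76 | 2.89 | 15.7% / 16.0% |
| Effect; 0.5 h per SD | 2.79 | 3.11 | 2.74 | 2.65 | 13.7% / 18.5% |
| Effect; 1 h per SD plus delayed closure | 2.78 | 3.39 | 2.65 | 2.58 | 16.8% / 26.1% |
| Effect; delayed closure only | 2.80 | 2.77 | 2.87 | 2.67 | 18.2% / 19.0% |
| No bleeding effect; 0.5 h saved, 0.5 h per SD | 1.00 | 0.87 | 0.87 | 0.86 | 9.0% / 18.8% |
| No bleeding effect; 1 h saved, 1 h per SD | 0.99 | 0.70 | 0.64 | 0.67 | 7.7% / 23.8% |
| No device effect at all; 0.5 h per SD plus delayed closure | 1.00 | 0.98 | 1.01 | 1.00 | 21.8% / 21.0% |

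The first row shows the simulation noise, roughly ±0.1. Against that, the rise to 3.1-3.4 in the shortest stratum is real.

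**5. Why the two illustrations differ in direction.** Conditioning on duration removes part of the device effect, but it also narrows the spread of bleeding within a stratum, which raises the win ratio. In step 4 the drainage effect is 320/253 = 1.26 SD, while the shift passed to duration is only 0.697 − 0.240 = 0.46 SD (the normal cut-points for 24.3% and 40.5%), so the second force can win. In step 3 duration carries the full 0.64 SD and the first force wins.

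**6. Stratum size.** With 65 per arm and the third row's shares, the >6 h stratum holds about 0.168 × 65 = 11 device and 0.261 × 65 = 17 control subjects.

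**The case against.** The case for leaving the SAP alone is substantial. The section is exploratory, uses only the word analyzed, names no test, and lies outside the fixed sequence in SAP 3.7 and 5.1. Most of the primary endpoint accrues after the duration clock stops: Protocol 9.2.1 counts UDPB drainage and red cell, platelet, plasma and cryoprecipitate transfusions from chest closure, and leaves out those products when given earlier. Planned surgery type is still analyzed. Every duration input above is assumed, and with about 11 and 17 subjects in a stratum, noise would swamp most of the distortion.

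All of that stands, and it rules out several stronger readings that a reader might infer:

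- *The SAP tests the primary endpoint in these strata.* No test is named.
- *The outcome forms the strata.* Only in part. The direct overlaps are delayed sternal closure and the factor products (PCC, rFVIIa) counted from the start of the procedure; planned surgery also drives duration.
- *Delayed closure lengthens the time by definition.* This needs a clock that runs to final sternal closure. SAP 1.3.7 says only closure, SAP 1.3.4 speaks both of the index operation and of completed chest closure, and Protocol Table 6 only has delayed closure recorded.
- *Item 1a replaces the planned-surgery stratum.* It is an addition to it.
- *The key secondary endpoint is distorted too.* This has not been shown. Its post-CPB sample is due within 30 minutes of disconnection, and the calculations cover only the primary composite.

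What does not stand is the view that an exploratory label settles the matter. It lowers the weight of the result but does not make the arms comparable. The SAP 3.6 sentence that disclaims a significance purpose applies to the list in that section, and procedure duration is not on it.

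**Conclusion.** The concern holds in limited form. Item 1a conditions on a post-randomization variable that is itself an endpoint, that the protocol expects the device to shorten, and that partly overlaps component 2. Stratum win ratios therefore cannot be read as effect modification.

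The size depends on the assumed duration-bleeding link. For Scenario 2 a uniform effect of about 1.9 appears as about 1.5-1.8. For Scenario 1 under a different structure, 2.8 becomes 2.6-3.4, so attenuation is usual but not general. The clearest case is a device that shortens surgery without reducing bleeding: apparent harm of about 0.57-0.87 in every stratum, against 1.0 overall. With no link, or with no device effect at all, there is no distortion; delayed closure alone contributes almost nothing. The main route is the expected effect on operative time, not the overlap with UDPB.

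The primary analysis, the sample size and type I error control are unaffected.

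**What to change.** Remove item 1a from SAP 1.3.7 as a treatment-effect subgroup for the primary endpoint and its components. Answer the operation-length question with planned surgery type, which is fixed before randomization and already a stratum. Keep operative time as an exploratory endpoint summarized by arm, as SAP 5.5 provides.

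If the table is kept, make two changes. State when the operative-time clock stops in a subject whose sternal closure is delayed. Label the table descriptive, with no causal or effect-modification reading. The same caveat belongs on CPB duration (item 1b): it ends before closure, but it is also measured after randomization.

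The cost is a line or two of SAP text and one exploratory table lost or relabelled.

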This study is a prospective, multi-center, double-blind, randomized pivotal trial to evaluate the safety and effectiveness of the DrugSorb™-ATR device to reduce postoperative bleeding as measured by a composite endpoint of: fatal perioperative bleeding (occurring within 48hrs of the index operation), moderate, severe, or massive bleeding (UDPB ≥ 2), and 24-hour chest tube drainage in patients undergoing cardiothoracic surgery requiring CPB within two days of ticagrelor discontinuation. Subjects will be randomized in a 1:1 ratio to either standard of care (SOC) alone (control arm) or standard of care plus intraoperative ticagrelor removal with DrugSorb™-ATR integration in the CPB circuit (investigational arm). In the control arm a sham device that is not actively connected to the CPB circuit will be placed in the identical location as the DrugSorb™-ATR device in the investigational arm, with the entire set-up covered by a drape to maintain the

blind. Subjects will be followed out to 30 days after the surgical procedure for assessments of adverse events (AE) and survival.

Prior to randomization, subjects will be stratified based on a) site, and b) type of planned cardiothoracic surgery [either CABG alone, or all other surgeries (including but not limited to combination cardiac procedures, and aortic interventions)]. Stratification is intended to control for confounding effects arising from differing institutional practices and from procedure-specific CPB duration (i.e., device exposure – treatment duration) and bleeding risk.

Number of subjects:

Up to 140 subjects will be randomized into the study (70 into each arm).

Number of sites:

Approximately 30 investigational sites in the US and Canada will participate in the study.

Subjects must meet all inclusion criteria to be eligible to participate in the study. Subjects meeting any of the exclusion criteria are not eligible to participate in the study.

Inclusion criteria:

1. Males and females aged ≥ 18
2. Written full informed consent
3. Cardiothoracic surgery requiring CPB within two days of ticagrelor discontinuation (**last day of completed ticagrelor treatment** = day 0):
 - CABG alone
 - Valve repair or replacement
 - Combination surgery (i.e., CABG + valve operation)
 - Aortic surgery

Exclusion criteria:

1. Cardiothoracic surgery occurring 3 days or greater following ticagrelor discontinuation
2. Heart-lung transplant procedures

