6.1. Pre-randomization Stratification

Pre-randomization stratification will be performed on two levels, based on the rationale described below:

1. By study site in order to control for differences in institutional protocols that could impact outcomes. These may include but are not limited to different institutional practices for drug and transfusion administration intra-op and post-op. Institutions may also differ in metrics utilized for clinical decision-making (e.g., delaying sternal closure, or surgical reoperation).
2. By the intended surgical procedure in order to control for differing procedure-specific

bleeding risks, and duration of CPB (i.e., device exposure) as detailed below:

- CABG alone (irrespective of number of grafts); or
- All other cardiothoracic procedures (including but not limited to combination procedures (i.e., CABG + aortic/mitral valve procedures, double heart valve procedures, etc.), aortic intervention, and combination aortic + cardiac interventions).

Of note, during the pre-procedure and intraoperative periods, the intended procedure may change due to factors that could not be adequately determined or anticipated in advance of the procedures. These day-of-surgery changes to the planned operations may result in the completion of a procedure that a) does not align with eligibility criteria, or b) alters stratification. Any change to the intended procedure occurring on the day of surgery that is not updated in the final IxRS assignment will be considered a protocol deviation. These protocol deviations will be noted in a deviation log for data analysis considerations at the conclusion of the trial. Subjects who have changes to their intended procedures on the day of surgery should progress through the study as in the protocol.

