6.2. Subject Randomization

All subjects will be prospectively randomized via an Interactive Voice/Web response (IxRS) system. Randomization must occur prior to the start of the cardiothoracic surgery procedure requiring CPB, but only after subject eligibility criteria is confirmed and written informed consent is provided by the subject or the subject's designated proxy. Subjects will be randomly assigned in a one to one (1:1) ratio to either the control arm (SOC) or the investigation arm (SOC + DrugSorb™-ATR device).

To ensure even distribution of subjects among the factors most likely to impact the primary and secondary outcomes they will undergo pre-randomization stratification based on study site (to account for different institutional protocols for bleeding and transfusion management), and type of surgery (isolated CABG – which generally has shorter CPB time, vs. all other cardiothoracic surgeries including combination cases – which generally require longer CPB times). Neither the investigator nor the subjects will be told their assignment prior to surgery. See below (**Section 6.3.1**) for details of the randomization assignment. A copy of the randomization assignment will be maintained in a confidential file maintained by the Randomization and Unblinding Administrator. If the subject withdraws consent following randomization but prior to surgery, the reason for failure to treat according to randomization will be recorded in the subject's study records.

To maintain the balance between sites in terms of numbers of subjects randomized, study sites will be capped at randomizing a maximum of 15% of the overall study sample. Sites may be allowed to randomize beyond the cap on a case-by-case basis in consultation with the sponsor, taking into account overall study goals, randomization balances between sites, and prior quality of data collected by the site.

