11. STATISTICAL CONSIDERATIONS

General statistical considerations: descriptive summaries will be presented using mean with standard deviation (SD), median, minimum and maximum for continuous variables and as count and percent of subjects for categorical variables. Inferential statistical tests will be two-sided, and use an alpha (α) critical value of 0.05, unless noted otherwise. Statistical analysis will be carried out using SAS Version 9.4 or later and/or R software language.

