#### 3.3 Randomization/Blinding

All subjects will be randomized in a one to one (1:1) ratio to either the control arm (SoC) or the treatment arm (SoC + DrugSorb™-ATR device). Pre-randomization stratification will be performed by study site, and by type of intended surgical procedure - either:

- CABG alone (irrespective of number of grafts); or
- All other cardiothoracic procedures (including but not limited to combination procedures [i.e., CABG + aortic/mitral valve procedures, double heart valve procedures, etc.], aortic interventions, and combination aortic + cardiac interventions).

Of note, patients undergoing undergo CABG + minor add-on procedures (e.g., left atrial appendage clipping, IABP or Impella placement, etc.) that do not (in the opinion of the investigator) significantly increase operative complexity or bleeding risk are included in the CABG alone category for Type of planned cardiothoracic surgery. Please see Section 6.1 of the CIP for additional details of pre-randomization stratification. Randomization is implemented via an Interactive Voice/Web response (IxRS) system.

Neither the subjects nor the site personnel have the treatment assignment information during the study period, unless specified in **Section 6.3** of the CIP. The blinded study team is blocked from every subject's treatment assignment before the data base lock for unblinding. Please see **Section 6.3** of the CIP for additional details of study blinding.

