#### **5.4.1 Continuous Secondary Effectiveness Endpoints**

The ANCOVA model with treatment group and type of surgery (when deemed appropriate) as covariates will be employed to assess the treatment difference in continuous secondary endpoints, unless specified otherwise.

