#### **5.4.1.2 Other Continuous Secondary Effectiveness Endpoints**

Total platelet/PRBC transfusions in volumes from end of operation through the duration of the index hospitalization (initial discharge from the hospital) will be analyzed based on the observed data using two-sample t test. The p-value and estimated mean difference along with the 95% CI will be provided between the treatment and control group.

Wilcoxon rank sum test based on the observed data in volumes will be performed if the normality assumption is invalid. The nonparametric p-value will be provided as well as median treatment difference in volumes for total platelet/PRBC transfusions.

The same analyses using transfusion data measured in units will be conducted as the supplemental analyses.

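### Randomisation is stratified by site, but the drainage and transfusion analyses leave site out; if site affects these outcomes, as the protocol expects, the tests are somewhat conservative and less precise than they could be.

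*Protocol*

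**What the plan says.** Protocol section 3 gives the reason for the site stratum: "Stratification by site is intended to control for institutional differences in standard practices, such as transfusion and re-operation protocols". Section 6.1 expects "different institutional practices for drug and transfusion administration intra-op and post-op" to differ between institutions, and section 6.2 gives the aim as "To ensure even distribution of subjects among the factors most likely to impact the primary and secondary outcomes". SAP section 3.3 confirms both factors: "Pre-randomization stratification will be performed by study site, and by type of intended surgical procedure". The synopsis plans for many sites: "Approximately 30 investigational sites in the US and Canada will participate in the study".

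The analyses are as follows.

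- **24-hour CTD.** Protocol section 11.3 uses a two-sample t-test. SAP sections 5.4.1 and 5.4.1.1 replace it: "The ANCOVA model with treatment group and type of surgery (when deemed appropriate) as covariates will be employed". Surgery type is therefore conditional, and site is absent.
- **Platelet and PRBC volumes.** SAP section 5.4.1.2 says these totals "will be analyzed based on the observed data using two-sample t test", with a Wilcoxon rank sum test if normality fails. Neither stratification factor appears.

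SAP sections 3.7 and 5.1 make CTD, platelets and PRBC consecutive steps in the fixed testing sequence, directly after the key secondary endpoint. Neither document gives a reason for omitting site, a block size, or an estimate of between-site variance.

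**The concern.** When arms are balanced within site, differences between sites largely cancel from the treatment comparison. The real sampling variance of the arm difference then falls below what a plain t-test assumes, because that test still counts between-site variation as noise. The reported standard error is too large, the confidence interval too wide, and the test rejects less than 5% of the time under the null.

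Transfusion volume is the outcome that the site rationale names most directly, yet it has the least adjusted analysis. The three endpoints are sequential, so a miss at one makes every later p-value nominal. What is at stake is precision on secondary claims. The point does not concern the primary Finkelstein-Schoenfeld test.

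**Working it through.** **Inputs from the documents.** Two-sided alpha is 0.05 (protocol section 11). About 30 sites take part, each capped at 15% of the sample (synopsis, section 6.2). The SAP expects 65 evaluable per arm, and the protocol's power figures use 57. Protocol section 11.1 plans CTD at 480 vs 800 mL (SD 253), platelets at 0.32 (SD 0.9) vs 1.6 (SD 2.2) units, and PRBC at 1.3 (SD 2.1) vs 4.4 (SD 5.7) units. SAP Table 1, scenario 2, raises the CTD SD to 500.

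**Assumed.** The share of outcome variance due to site (ICC) runs from 0 to 0.30, blocks are of 2 or 4 within site by surgery type, and 80% of subjects have CABG alone.

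**Step 1: reproduce the stated power at 57 per arm.** Power comes from the noncentral t with noncentrality difference/SE, where SE = √(SD₁²/n + SD₂²/n).

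- Platelets: SE = √(0.9²/57 + 2.2²/57) = 0.315; 1.28/0.315 = 4.07; power 98.0% (stated 98.0%).
- PRBC: SE = √(2.1²/57 + 5.7²/57) = 0.805; 3.1/0.805 = 3.85; power 96.7% (stated 96.7%).
- CTD at SD 253: SE = 253√(2/57) = 47.4; 320/47.4 = 6.75; power >99.99% (stated >99.9%).

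At 65 per arm the same formulas give platelets 99.0%, PRBC 98.2%, and CTD >99.99% at SD 253 or 95.2% at SD 500 (SE 87.7, noncentrality 3.65).

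**Step 2: bound the effect on size.** With perfect balance within site, the true SE is the t-test SE times √(1 − ICC), so size = 2Φ(−1.96/√(1 − ICC)). This gives 4.4%, 3.9%, 2.8% and 1.9% at ICC 0.05, 0.10, 0.20 and 0.30. Incomplete blocks at small sites weaken the balance, so the real figures should lie between these and 5%.

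**Step 3: simulate.** Trials had 130 subjects at 30 unequal sites capped near 15%, permuted blocks within strata, normal outcomes with total SD 500, and 2,000–6,000 replicates per cell. Monte Carlo error is about 0.3 points on size and up to about 1 point on power. The upper end of the size range at ICC 0.30 comes from a separate simulation with blocks of 4. The power columns use blocks of 2 and show the analysis without site, then with a random site intercept.

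| Site ICC | True size without site | Power, CTD 320 mL | Power, 245.6 mL (about 80% nominal) |
|---|---|---|---|
| 0.05 | 4.3–4.9% | 95.3 → 95.9% | 81.4 → 83.0% |
| 0.10 | 4.1–4.6% | 95.7 → 96.5% | 80.7 → 83.0% |
| 0.20 | 3.4–3.7% | 96.3 → 98.0% | 81.6 → 85.7% |
| 0.30 | 2.5–3.1% | 97.4 → 99.0% | 82.8 → 89.9% |

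At ICC 0 the size without site was 4.6–5.3%. Models with site ranged from 4.4% to 5.6%. As a check on the mechanism, at ICC 0.30 with blocks of 2 the empirical SE was 77.6 against a model SE of 86.8. The ratio 0.894 implies a size of 2Φ(−1.96/0.894) = 2.8%, against 2.6% simulated.

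**Step 4: form of the adjustment.** About 30 site fixed effects gave 78.9% against 80.5% for the covariate model without site at ICC 0.05 (blocks of 2, the 80% effect), and 80.2% against 79.4% at ICC 0.10. They gained clearly only from about ICC 0.20.

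**Step 5: transfusions at the planned effects.** Power without site is already 99.0% and 98.2%, so no adjustment can add more than 1.0 and 1.8 points.

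**The case against.** The strongest reply is that the plan is valid as it stands. The omission does not bias the estimate or inflate type I error. The stated powers reproduce, and balanced allocation does not reduce them: at SD 500, unadjusted CTD power in simulation was about 95–97%, against 95.2% nominal. At the planned effects these steps in the sequence pass roughly 95–99% of the time or more. All of this stands.

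A reader might infer that these tests do run below 5%. The documents do not support that as fact, because they give neither a site variance nor a block size. At an ICC of 0.05 the shortfall is at most about 0.7 points, barely distinguishable from simulation error.

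A reader might also infer that stratification was meant to buy precision that is now wasted. The protocol speaks of controlling confounding and distributing subjects evenly, and balanced allocation serves those aims without a site term.

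The site rationale names transfusion and re-operation practice, so the case for CTD is weaker. Section 6.2 does refer to secondary outcomes in general.

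On the other side, the planned transfusion effects are large: 80% for platelets (1.6 to 0.32) and 70% for PRBC (4.4 to 1.3). Protocol Table 3 discounts the other bleeding effects to about 40%. As an illustration only, a 40% reduction with the protocol's SDs and 65 per arm gives about 57% power for platelets and 64% for PRBC. Extra precision could then matter.

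**Conclusion.** The point holds in conditional form and is a cheap improvement, not a validity defect. Site is a randomisation factor with a stated prognostic reason, and it is missing from three endpoints in the testing sequence. The transfusion tests omit surgery type as well.

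If site carries 10–30% of the variance, true size is about 4.6% down to 2.5%. The cost relative to a random-intercept analysis is about 1–2 points for CTD at the planned effect with SD 500, negligible at SD 253, and at most about 1–2 points for transfusions at the planned effects. Near 80% power it is about 2–7 points. If site explains nothing, the choice makes no material difference.

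It would be wrong to read this as inflated false positives or as overstated planned power for these tests; the calculations show neither.

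The size and power figures rest on the assumed ICC, block sizes and site distribution, and on normal outcomes. Skewed transfusion data were not modelled in the table above. A Wilcoxon test on the normal data did show the same fall in size (2.8% at ICC 0.30, blocks of 2).

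**What to change.** In SAP sections 5.4.1, 5.4.1.1 and 5.4.1.2, analyse 24-hour CTD, platelet volume and PRBC volume with:

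- treatment;
- planned surgery type as entered in the randomisation system (IxRS), included unconditionally;
- a random intercept for site, with its variance set to zero if it cannot be estimated, and a stated degrees-of-freedom method.

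Do not use about 30 site fixed effects. If the rank fallback is kept, prespecify a site-aligned or stratified rank test, and check its size by simulation on skewed data first, since it has not been tested here. If site is to stay out, the SAP should say why.

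The cost is SAP wording and one mixed model per endpoint, with no new data. The downside is one extra variance parameter, estimated with about 4–5 subjects per site (130/30 = 4.3).
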